10 DEFINITION OF ENDPOINTS

10.1 PRIMARY EFFICACY ENDPOINT

Objective response (OR = CR+PR) measured by CT and assessed per RECIST 1.1. Complete response (CR) and partial response (PR) require confirmatory CT repeat assessment at least 4 weeks after the first detection of response.

10.2 SECONDARY EFFICACY ENDPOINTS

1) **Duration of response** (DOR) as measured from the date of first response (CR or PR) to date of disease progression (taking as reference for progressive disease the smallest measurements recorded since the treatment started) or death.

2) **Disease control rate** (DCR) based on patient who had CR or PR or Stable disease (SD) for at least 2 cycles (8 weeks).

3) **Best overall response** (BOR) determined from a sequence of responses assessed. Two objective status determinations of CR before progression are required for a BOR of CR. Two determinations of PR or better before progression, but not qualifying for a CR, are required for a BOR of PR. A minimum timeframe of 8 weeks is required for a BOR of SD.

3) **Progression free survival** (PFS) as measured from the date of first study drug dose to the date of the first objective documentation of radiographic disease progression or death due to any cause.

4) **Overall survival** (OS) as measured from the date of first study drug dose to the date of death by any cause.

10.3 SAFETY ENDPOINTS

Primary safety endpoints are Dose-limiting toxicities, treatment-emergent adverse events, clinically significant changes in vital signs, electrocardiograms (especially QT), laboratory parameters (hematology, serum chemistry, urinalysis, serum pregnancy test), physical examination results.

10.4 EXPLORATORY ENDPOINTS

- 1) To evaluate the utility of detection of KRAS G12C mutations in plasma ctDNA to identify the study population.
- 2) To explore the association between baseline tumor biomarkers, gene alterations and clinical activity.
- 3) To identify known and possibly new markers of resistance to KRAS G12C inhibition in baseline tumor tissue (if available) including phosphorylated ERK and S6 kinase.
- 4) To examine mutations in *RAS* and other tumor genes potentially implicated in the resistance to sotorasib using ctDNA.

11 STATISTICAL CONSIDERATIONS

11.1 STUDY DESIGN

Study CTO # 103048 is a potentially multicenter, non-randomized, single cohort phase IB trial evaluating the safety and efficacy of tarloxotinib in combination with sotorasib in NSCLC patients with KRAS G12C mutation who have progressed on any small molecule KRAS G12C inhibitor.

Safety lead-in

A minimum of 6 patients and as many as 18 patients will be enrolled in a safety lead-in cohort to evaluate the safety of the combination of tarloxotinib and sotorasib. Sotorasib will be held at a fixed dose of 960 mg QD (the approved dose) while the starting dose of tarloxotinib will be the monotherapy RP2D equal to 150mg/m² QW (dose level 1 [DL1]). Following a 3+3 algorithm, an initial 3 patients will be enrolled at DL1. If 0 or 1 of 3 patients experience a DLT, an additional 3 patients will be enrolled to DL1. DL1 will be declared the combination RP2D (RP2D_c) if at most 1 of 6 patients treated at DL1 experience a DLT. Alternatively, if there are 2 or more DLTs observed at DL1, 3 patients will be enrolled at DL -1 and the 3+3 rules repeated for safety evaluation. The RP2D_c will be the highest DL at which at most 1 patient of 6 experiences a DLT. If DL -2 is considered too toxic, additional dose levels below DL -2 to be determined may be considered for safety.

Dose expansion

Once the tarloxotinib RP2D_c is reached, an expansion cohort of up to 12 patients will be enrolled to evaluate the safety of the combination of tarloxotinib and sotorasib. Eligible safety lead-in patients treated at the RP2D_c will be included in the expansion cohort.

The combination of tarloxotinib and sotorasib will not be considered promising if there is weak evidence the true objective response rate (ORR) exceeds 20%. Specifically, the trial will be declared negative if $\text{Prob}(\text{true ORR} > 20\% | \text{observed no. of responses}) < 20\%$, equivalent to observing at most 1 response in 12 patients. We assume the true ORR follows a beta (0.5, 0.5) prior distribution and, conditional on the true ORR, the number of responses follows a binomial distribution. If at least 2 responses in 12 patients are observed, the combination may be considered promising. Given 1 response in 12 patients, the probability the true ORR exceeds 20% is approximately 16%. Given 2 responses in 12 patients, the probability the true ORR exceeds 20% is approximately 42%.

11.1.1 SAMPLE SIZE DETERMINATION

The sample size of 6 patients in the safety lead-in and 12 patients in the expansion cohort will allow for preliminary assessment of safety and anti-tumor activity at the RP2D_c. For primary safety outcomes, the table below shows the probability of observing at least one DLT/DLT-equivalent (DLT-E) for true DLT/DLT-E rates ranging from 10% to 40% for group sample sizes of 6 (safety lead-in cohort) and 12 (expansion cohort). (A DLT-equivalent is any safety event that would have qualified as a DLT had that patient been enrolled in the safety lead-in portion of the study.)

Probability of observing at least 1 DLT/DLT-equivalent events for n = 6 or 12.

True DLT/DLT-E rate	Probability of observing ≥ 1 DLT/DLT-Es	
	n=6	n=12
0.05	0.26	0.46
0.10	0.47	0.72
0.15	0.62	0.86
0.20	0.74	0.93
0.25	0.82	0.97
0.30	0.88	0.99

For the 12 patients in the expansion cohort, example incidence rates and corresponding exact 95% binomial confidence intervals (CIs) summarizing safety (e.g., AE or DLT-E rates) or response (e.g., ORR or DCR) are shown in the table below. The values are provided as a reference for estimation rather than as a basis for any decision criteria. The RP2D_c may be revised based on accumulated safety data obtained in expansion.

Estimated incidence rate and exact binomial 95% CI for n = 12.

No. of Cases	Estimated Rate	95% CI	
		Lower Limit	Upper Limit
0	0	0	0.26

1	0.08	0.00	0.38
2	0.17	0.02	0.48
3	0.25	0.05	0.57
4	0.33	0.10	0.65
5	0.42	0.15	0.72
6	0.5	0.21	0.79

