11.3 INTERIM ANALYSES

Safety lead-in

Safety and tolerability data will be reviewed on a cohort-by-cohort basis during safety lead-in to determine if an additional cohort of patients should be enrolled at the current DL, if de-escalation is warranted, or if the protocol should be amended to evaluate additional intermediate or lower DLs. The final determination of the RP2D_c will be based on the totality of data including, but not limited to, safety and early signs of anti-tumor activity.

Dose expansion

Interim futility analysis. Given the limited sample size, there will be no futility interim analysis in the dose expansion cohort.

Continuous safety monitoring. Bayesian toxicity monitoring will be used to perform continuous safety monitoring of patients enrolled in the expansion cohort. Specifically, patients enrolled in the expansion cohort will be monitored for incidence of DLT-equivalent (DLT-E) events, defined as any safety event that would have qualified as a DLT had that patient been enrolled in the safety lead-in portion of the study. We assume the true DLT-E rate follows a beta (0.5, 0.5) prior distribution and, conditional on the true DLT-E rate, the number of patients who experience a DLT-E follows a binomial distribution. If $\text{Prob}(\text{DLT-E rate} > 33\% | \text{observed no. DLT-Es}) > 50\%$, trial enrollment will be paused. (Note: The observed number of DLT-Es will include DLTs from eligible safety lead-in patients treated at the RP2D_c who are included in the expansion cohort. Bayesian toxicity monitoring parameters were selected to calibrate with the 3+3 de-escalation rules used in the safety lead-in.) If the trial is paused, the safety review committee will review the totality of the safety data and determine whether to continue patient enrollment at the current RP2D_c, introduce intermediate or lower dose levels for evaluation, or close the trial to accrual and declare the combination of tarloxitinib and sotorasib too toxic. This monitoring rule has a 13% and 95% probability of pausing if the true DLT-E rate is 10% or 50%, respectively. The table below specifies safety monitoring thresholds.

Bayesian toxicity monitoring boundaries		
No. of patients	No. of DLT-Es to pause study	Observed DLT-E rate
6	≥2	≥0.33
7-9	≥3	≥0.33
10-11	≥4	≥0.36
12 – expansion cohort fully accrued		

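### The 12-patient DLT-E figures in section 11.1.1 ignore that up to six patients come from a level chosen for having at most 1 DLT in 6, so the pooled rate is biased low

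*Combined protocol and SAP*

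**What the plan says.** **Selection of the level (section 11.1, Safety lead-in).** "If 0 or 1 of 3 patients experience a DLT, an additional 3 patients will be enrolled to DL1" The level then passes on six patients: "DL1 will be declared the combination RP2D (RP2D_c) if at most 1 of 6 patients treated at DL1 experience a DLT". The general rule is the same: "The RP2D_c will be the highest DL at which at most 1 patient of 6 experiences a DLT".

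**Pooling (section 11.1, Dose expansion).** The expansion cohort is up to 12 patients, and "Eligible safety lead-in patients treated at the RP2D_c will be included in the expansion cohort".

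**Counting (section 11.3, Continuous safety monitoring).** "The observed number of DLT-Es will include DLTs from eligible safety lead-in patients treated at the RP2D_c who are included in the expansion cohort". The monitoring table starts at 6 patients and ends with "12 – expansion cohort fully accrued", which points to six carried over plus six new.

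**Use of the pooled 12 (section 11.1.1).** One table gives the probability of at least one DLT or DLT-E for n=6 and n=12. A second, for the 12 expansion patients, gives example rates with "exact 95% binomial confidence intervals (CIs) summarizing safety (e.g., AE or DLT-E rates", so DLT-E rates are named among the quantities covered. The same section calls these values a reference for estimation and not a basis for decisions.

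Section 11.2.4 lists a summary of DLTs and DLT-Es in the safety analysis set and names no interval. No section mentions that the carried-over patients were selected on the outcome being estimated, and none plans a separate DLT-E rate for newly enrolled patients.

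**The concern.** Half of the 12 may be in the cohort only because their group showed 0 or 1 DLT. A group with 2 or more of 6 never becomes the RP2D_c group, so the upper part of the lead-in distribution is cut off. The other six patients are unselected. A plain proportion over all 12 mixes the two and sits below the true rate on average.

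Safety and the RP2D form a primary objective, DLTs are the first endpoint listed under it, and section 11.1.1 allows the RP2D_c to be revised on safety data from expansion. A reader who takes the pooled rate as an ordinary binomial estimate would think the level safer than the data show.

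**Working it through.** **Inputs.** Six lead-in patients at the selected level, rule at most 1 DLT in 6 (section 11.1); 12 in total, so six new (sections 11.1 and 11.3); two-sided 95% exact binomial interval (section 11.1.1). The true DLT-E rate p is not given. I use 5% to 50%, which covers the plan's table (5% to 30%), its 33% pause bound and its 50% scenario. Patients are taken as independent.

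**The plan's own figures reproduce.** 1 − (1−p)^12 gives 0.46, 0.72, 0.86, 0.93, 0.97 and 0.99 at 5% to 30%, as printed. Clopper-Pearson limits for n=12 also match, for example 0/12: 0 to 0.265; 1/12: 0.002 to 0.385; 2/12: 0.021 to 0.484.

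**Conditioning on the lead-in.** Write q = 1−p, and let X be the number of DLTs among the six lead-in patients.

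- Chance that the level passes: q^6 + 6pq^5 = q^5(1+5p).
- Mean DLTs among the six, given a pass: 6p/(1+5p).
- Expected pooled rate: [6p/(1+5p) + 6p]/12.
- Chance of at least one DLT-E in 12, given a pass: 1 − q^7/(1+5p).

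At p = 0.33: 6p/(1+5p) = 1.98/2.65 = 0.747, so the pooled rate is (0.747 + 1.98)/12 = 0.227. The pass probability is 0.67^5 × 2.65 = 0.358.

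At p = 0.20: 1.2/2 = 0.6, so the pooled rate is (0.6 + 1.2)/12 = 0.150. The chance of at least one event is 1 − 0.8^7/2 = 0.895.

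| True rate | Level passes | Expected pooled rate | P(≥1 in 12), printed | P(≥1 in 12), given pass |
|---|---|---|---|---|
| 5% | 97% | 4.5% | 0.46 | 0.44 |
| 10% | 89% | 8.3% | 0.72 | 0.68 |
| 15% | 78% | 11.8% | 0.86 | 0.82 |
| 20% | 66% | 15.0% | 0.93 | 0.90 |
| 25% | 53% | 18.1% | 0.97 | 0.94 |
| 30% | 42% | 21.0% | 0.99 | 0.97 |
| 33% | 36% | 22.7% | – | – |
| 40% | 23% | 26.7% | – | – |
| 50% | 11% | 32.1% | – | – |

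**Interval coverage, by exact enumeration given a pass.**

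- At 5% to 25%, coverage is at least 99%, and the upper limit never falls below the true rate.
- At 30%, 33%, 35% and 38% it is 96.7%, 97.7%, 98.2% and 98.8%. Between these points it dips to about 95.0% just above 26.5%, where 0/12 starts to miss: 0.735^7/2.325 = 0.050.
- At 40% both 0/12 and 1/12 miss. P(0) = 0.6^7/3 = 0.009 and P(1) = 0.2 × 0.187 + 0.8 × 0.047 = 0.075. Coverage is therefore 91.6%. At 50% it is 85.7%. At both rates every miss has the upper limit too low.

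**Precision of the alternative.** Root mean squared error given a pass, pooled 12 against the six new patients alone: 0.104 against 0.163 at 20%; 0.145 against 0.192 at 33%; 0.170 against 0.200 at 40%; about equal at 50%.

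**The case against.** The strongest reply is that the target is an illustrative table. Section 11.1.1 labels it as reference, section 11.2.4 plans no interval for DLT-Es, and the only formal DLT-E inference is the beta-binomial monitoring in section 11.3, whose posterior is not changed by the selection. Levels with high true rates seldom pass, and at 10% to 20% the bias is 2 to 5 points, against intervals 38 to 46 points wide for 1 or 2 cases in 12. The pooled estimate also has the smaller error until about 50%. All of this stands, and it limits the weight of the point. It does not remove it: section 11.1.1 names DLT-E rates as something these figures describe, and estimation is where the bias arises.

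The truncation model is also idealised. Section 11.3 bases the final RP2D_c on the totality of data, and fewer than six lead-in patients may prove eligible. If the cohort meant 12 new patients plus six, a true 33% would average 26.2% over 18. The monitoring table favours six plus six.

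A reader might infer more than the documents support:

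- **That the interval is unsafe in general.** It is not. At 5% to 25% no miss has the upper limit too low, and two-sided coverage does not fall materially below 95% until about 38%. One-sided misses do exceed 2.5% from about 26.5% to 32%.
- **That the printed numbers are miscalculated.** They are correct for 12 unselected patients.
- **That DLT-E should leave the interval table, or that the six-patient rate should replace the pooled one.** The error comparison argues against both.

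**Conclusion.** The point holds for the pooled estimate and for the n=12 column of the at-least-one table. Given a pass, the pooled DLT-E proportion is low by 1.7 points at a true rate of 10%, 5.0 at 20%, 9.0 at 30% and 10.3 at 33%. The n=12 column is too favourable by about 0.02 to 0.04. The interval is a secondary matter, with a clear shortfall only at high rates that pass the lead-in no more than about a quarter of the time.

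This rests on independent patients, six carried forward, six new, and strict use of the at-most-1-of-6 rule. It concerns DLT-Es. Response, disease control and other adverse events are affected only as far as they correlate with DLTs. The change is worth making because it bears on a primary safety result, but nothing here shows that a dose or stopping decision in the plan is wrong.

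**What to change.** 1. Keep the pooled n=12 DLT-E rate and interval, and state in sections 11.1.1 and 11.2.4 that they are conditional on the level having passed the lead-in.
2. Beside them, report the DLT-E rate and exact interval for newly enrolled expansion patients as a sensitivity summary, noting its lower precision. With six patients the intervals are 0 to 0.46 for 0/6, 0.004 to 0.64 for 1/6 and 0.04 to 0.78 for 2/6.
3. Optionally add a selection-adjusted pooled estimate, solving 6p/(1+5p) + 6p = total DLT-Es, with exact conditional limits. For 1, 2 and 3 events this gives 0.10 (0.002 to 0.51), 0.23 (0.02 to 0.66) and 0.37 (0.07 to 0.79), against plain rates of 0.08, 0.17 and 0.25.
4. Restate the n=12 column as conditional on passing (0.44, 0.68, 0.82, 0.90, 0.94, 0.97 at 5% to 30%), or label it as assuming 12 unselected patients.

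The cost is one or two table rows and a few sentences. Enrolment, dosing and the monitoring rule are untouched.

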11.1.2 POPULATIONS FOR ANALYSES

The following analysis sets will be defined for this study.

The **safety analysis set** comprises all enrolled patients who receive any quantity of study treatment, regardless of eligibility. The safety evaluation will be performed based on the first dose of study treatment a patient receives, regardless of the patient's cohort assignment. The safety analysis set will be used for all dosing/exposure and safety analyses.

The **DLT-evaluable population (safety lead-in only)** comprises patients who have either completed the DLT-observation period (1 cycle, 28 days) and received at least 75% of planned doses of the tarloxotinib and sotorasib combination in cycle 1 or have discontinued study treatment or study participation before completing cycle 1 due to a DLT.

The **intention to treat (ITT) analysis set** comprises all patients in the safety analysis set eligible for study inclusion and who meet the inclusion criteria for dose expansion, including eligible safety lead-in patients treated at the RP2D_c. This analysis set will be used for all efficacy analyses.

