Statistical Methods	
Analysis Populations
 
The following analysis sets will be defined for this study.
 
The safety analysis set comprises all enrolled patients who receive any quantity of study treatment, regardless of eligibility. The safety evaluation will be performed based on the first dose of study treatment a patient receives, regardless of the patient's cohort assignment. The safety analysis set will be used for all dosing/exposure and safety analyses.

[figure not shown]
	
The DLT-evaluable population (safety lead-in only) comprises patients who have either completed the DLT-observation period (1 cycle, 28 days) and received at least 75% of planned doses of the tarloxotinib and sotorasib combination in cycle 1 or have discontinued study treatment or study participation before completing cycle 1 due to a DLT.
 
The intention to treat (ITT) analysis set comprises all patients in the safety analysis set eligible for study inclusion and who meet the inclusion criteria for dose expansion, including eligible safety lead-in patients treated at the combination RP2D. This analysis set will be used for all efficacy analyses.
 
Safety lead-in
 
A minimum of 6 patients and as many as 18 patients will be enrolled in a safety lead-in cohort to evaluate the safety of the combination of tarloxotinib and sotorasib. Sotorasib will be held at a fixed dose of 960 mg QD (the approved dose) while the starting dose of tarloxotinib will be the monotherapy RP2D equal to 150mg/m² QW (dose level 1 [DL1]). Following a 3+3 algorithm, an initial 3 patients will be enrolled at DL1. If 0 or 1 of 3 patients experience a DLT, an additional 3 patients will be enrolled to DL1. DL1 will be declared the combination RP2D (RP2D_c) if at most 1 of 6 patients treated at DL1 experience a DLT. Alternatively, if there are 2 or more DLTs observed at DL1, 3 patients will be enrolled at DL -1 and the 3+3 rules repeated for safety evaluation. The RP2D_c will be the highest DL at which at most 1 patient of 6 experiences a DLT. If DL -2 is considered too toxic, additional dose levels below DL -2 may be evaluated for safety.
 
Dose expansion
 
Once the tarloxotinib RP2D_c is reached, an expansion cohort of up to 12 patients will be enrolled to evaluate the safety of the combination of tarloxotinib and sotorasib. Eligible safety lead-in patients treated at the RP2D_c will be included in the expansion cohort.

--	---

TABLE OF CONTENTS

1	SCHEMA	6

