6.2 DEFINITION OF DOSE-LIMITING TOXICITY (DLT)

Toxicities will be graded according to the NCI Common Toxicity Criteria scale version 5.0. If multiple toxicities are seen, the presence of DLT should be based on the most severe toxicity grade experienced. DLT will be defined as any of the following events occurring during treatment with study drugs and is deemed possibly, probably or definitely attributable to the study drugs:

- Any Grade 3 or 4 thrombocytopenia, anemia and/or neutropenia.
- Any other non-hematologic Grade 3 or 4 toxicity that is clinically significant, excluding alopecia.
- Any grade 3 nausea, vomiting or diarrhea that persists > 72 hours despite the use of maximal medical intervention and/or prophylaxis as indicated by good clinical practice and the judgment of the investigator.
- Any grade 4 vomiting or diarrhea regardless of duration.
- Failure to recover from toxicities to be eligible for re-treatment within 4 weeks.
- Any death not clearly due to the underlying disease or extraneous causes, and for any toxicity requiring permanent discontinuation of study drug(s).
- Hy's law, defined as: AST or ALT > 3 x the upper limit of normal (ULN) with concurrent increase in total bilirubin > 2 x ULN without evidence of cholestasis or alternative explanations, (e.g., viral hepatitis, disease progression in the liver, etc.)
- Neutropenic fever

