6.5.2 Tarloxotinib Dose Modifications

All patients will receive a weekly tarloxotinib infusion at the RP2Dc determined in the safety lead-in portion of the trial administered as a weekly 1-hour IV infusion on Days 1, 8, 15, and

22 of each 28-day cycle until disease progression or unacceptable toxicity. All patients will begin study treatment based on the body weight measured on Day 1 of each cycle (or within 7 days prior [e.g., Day 22 of the prior cycle]). As described above, tarloxotinib dose calculations do not need to be adjusted within a cycle unless the patient has a > 10% change in body weight. Other dose modifications may be required based on QTc prolongation, infusion-related reactions, and other tarloxotinib-related toxicity as described below.

Dose level reductions will be in a step-wise fashion. If a patient requires more than 2 dose level reductions, tarloxotinib will be permanently discontinued.

Hematologic toxicity has not been associated with tarloxotinib administration to date. However, if Grade 3 or 4 neutropenia or thrombocytopenia considered related to tarloxotinib occurs, then the treatment guidelines for non-hematologic toxicity should be followed. Dose modifications for anemia (any grade) or for Grade 2 or less neutropenia or thrombocytopenia are not required.

If a tarloxotinib-related toxicity results in a treatment delay of more than 3 weeks (withholding more than 2 doses of tarloxotinib), patients will be removed from study treatment unless otherwise approved by the Principal Investigator.

Should a dose reduction for sotorasib be required, given the potential for overlapping toxicities and challenges in attributing toxicities to one drug in a combination therapy, a dose reduction in tarloxotinib should also be considered.

Dose level	Sotorasib	Tarloxitinib
0 (full dose)	960 mg PO daily	150 mg/m ² IV weekly
-1	480 mg PO daily	100 mg/m ² IV weekly
-2	240 mg PO daily	75 mg/m ² IV weekly

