6.5.6 Treatment Guidelines for Other Non-Hematologic Toxicity

The table below provides treatment guidelines for treating tarloxitinib non-hematologic toxicities other than QT prolongation and infusion-related reactions.

Toxicity (CTCAE v5.0)	Details	Hold Dose	Dose Levels After Recovery to \leq Grade 2 or Baseline
Grade 2	Intolerable skin toxicity or diarrhea	Hold dose until resolution to Grade 0 or 1 or Grade 2 tolerable	If symptoms are intolerable, recurrent, or not controlled by supportive care, hold dose until symptoms improve and reduce to next lower dose level
Grade 2	ALT or AST $> 3 \times$ ULN	Hold dose until resolution to $<$ Grade 2 or baseline	150 mg/m ² (no reduction)
	ALT or AST $> 3 \times$ ULN (Grade 2) AND a total bilirubin $\geq 2 \times$ ULN (patients without liver metastasis)**	Treatment to be discontinued	Not applicable
Grade 3	Nausea and vomiting*	Hold dose until resolution to Grade 0 or 1 or Grade 2 tolerable	120 mg/m ² ; if recurs, then second reduction to 75 mg/m ²
Grade 4	Pulmonary embolism that is adequately treated	Hold dose until resolution to Grade 0 or 1	120 mg/m ² ; if recurs, then second reduction to 75 mg/m ²
Grade 4	All other life-threatening conditions	Treatment to be discontinued	Not applicable

ALT = alanine aminotransferase; ASP = aspartate aminotransferase; CTCAE = Common Terminology Criteria for Adverse Events; ULN = upper limit of normal

* May hold or reduce if nausea/vomiting continues despite optimized anti-emetic treatment

** Tarloxitinib-related toxicity meeting the definition of Hy's Law, tarloxitinib will be discontinued permanently

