7.1.5 Dose Delays

All dose schedule modifications of > 1 day must be discussed with the Principal Investigator (or designee). Intentional cycle delays of > 1 day (e.g., patient vacation, physician requested “drug holiday”) must be approved by the Principal Investigator (or designee). Study visits will align with tarloxotinib infusion days. If a tarloxotinib dose must be delayed > 3 days, this will be considered a missed dose.

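### The DLT-evaluable definition leaves out a lead-in patient whose cycle 1 DLT leads to a dose hold below 75% without discontinuation, so a 3+3 counted on that set would drop the DLT

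*Combined protocol and SAP*

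**What the plan says.** Section 11.1.2, repeated in the Statistical Methods part of the synopsis, gives two routes into the DLT-evaluable population. The core of the definition is "received at least 75% of planned doses of the tarloxotinib and sotorasib combination in cycle 1 or have discontinued study treatment or study participation". The first route is for patients who complete the 28-day observation period with enough treatment. The second is for those who "have discontinued study treatment or study participation before completing cycle 1 due to a DLT".

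The dose-finding rule is in 11.1. The first dose level becomes the RP2D_c "if at most 1 of 6 patients treated at DL1 experience a DLT". The other branch of the rule reads: "if there are 2 or more DLTs observed at DL1, 3 patients will be enrolled at DL -1". Neither sentence mentions the DLT-evaluable set, and no section says what that set is used for. Section 11.1.2 assigns all exposure and safety analyses to the safety analysis set, and 11.2.4 lists DLTs among the summaries made on that set.

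Several management rules let a patient with a toxicity pause and resume. For Grade 3 nausea and vomiting, 6.5.6 says "Hold dose until resolution to Grade 0 or 1 or Grade 2 tolerable", and 7.2.8 has a parallel hold for sotorasib. Under 6.5.2 it takes a "treatment delay of more than 3 weeks (withholding more than 2 doses of tarloxotinib), patients will be removed from study treatment", unless the Principal Investigator approves otherwise. Section 7.1.5 adds: "If a tarloxotinib dose must be delayed > 3 days, this will be considered a missed dose".

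**The concern.** A DLT-evaluable set normally keeps every patient who had a DLT and removes only DLT-free patients who were under-exposed. Here a patient who had the DLT must also either reach the 75% threshold or discontinue within cycle 1. A patient who is held for the DLT and resumes late in the cycle may do neither. Exclusion by this route requires the event itself, so it can act in one direction only: the counted DLT rate falls.

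DLTs and the RP2D_c belong to the first primary objective, and the rule turns on whether one or two of six patients have a DLT. One reclassified patient can therefore change the numerical answer. A statistician could reasonably run the 3+3 on the DLT-evaluable set. It is defined for the lead-in only, it is given no other purpose, and its definition is the only place where the 28-day DLT period is stated; 6.2 refers only to events during treatment.

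**Working it through.** **1. The plan's own figures.** No figure is attached to the evaluability definition. The nearest ones reproduce:
- The chance of at least one DLT in six patients, 1 − (1 − p)^6, is 0.2649, 0.469, 0.623, 0.738, 0.822 and 0.882 for p = 0.05 to 0.30. Section 11.1.1 prints 0.26, 0.47, 0.62, 0.74, 0.82 and 0.88.
- The pausing probabilities in 11.3 come out at 12.6% and 95.0%, against the stated 13% and 95%.

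**2. Can such a patient arise?** Grade 3 vomiting lasting more than 72 hours despite maximal intervention is a DLT under 6.2. It falls in a hold row for tarloxotinib (6.5.6, where a footnote permits either a hold or a reduction) and for sotorasib (7.2.8). Suppose both drugs are held from Day 15 through Day 22.
- The Day 15 infusion is delayed by more than 3 days, so it is missed.
- The Day 22 infusion can still be given on Day 23, within the 1-day visit window.
- The 3-week removal rule is not reached.
- Sotorasib is missed on 8 days.

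**3. Exposure.** Inputs are 4 infusions (7.1.4) and 28 daily sotorasib doses, so 4 + 28 = 32 pooled. The 75% threshold is then 3 infusions, 21 sotorasib days or 24 pooled doses. Planned is taken here as the full schedule.

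| Missed in cycle 1 | Infusions | Sotorasib | Pooled | At least 75%? |
|---|---|---|---|---|
| 2 infusions | 2/4 = 50% | 28/28 | 30/32 = 94% | no per drug; yes pooled |
| 8 sotorasib days | 4/4 | 20/28 = 71% | 24/32 = 75% | no per drug; yes pooled |
| 1 infusion + 7 days | 3/4 = 75% | 21/28 = 75% | 24/32 = 75% | yes on both |
| 1 infusion + 8 days | 3/4 = 75% | 20/28 = 71% | 23/32 = 72% | no on both |

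The last row is the patient in step 2. This patient completes the 28 days below 75% and does not discontinue, so neither route applies.

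**4. Two counts on the same data (illustration).** Six patients are treated at the first dose level. Two have a DLT, and one of these two is held as above.
- Treated count: 2 of 6, so de-escalate.
- Evaluable count: 1 of 5, which does not literally satisfy a rule written for six.
- With a DLT-free replacement added: 1 of 6, so the level is accepted. The plan contains no replacement rule.

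If the level is accepted, 11.3 counts the DLTs of eligible lead-in patients under a beta(0.5, 0.5) prior. For 2 of 6 the posterior is Beta(2.5, 4.5) and P(rate > 33%) = 0.53, above the 50% trigger, so enrollment pauses. With the replacement it is 2 of 7: the posterior is Beta(2.5, 5.5), the probability is 0.42, and there is no pause.

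**5. Hypothetical sensitivity.** Let h be the share of DLT patients who fall in the gap. The documents do not give it. Assume also that dropped patients are replaced. The apparent DLT rate is q = p(1 − h)/(1 − ph), and the chance that a level is accepted is (1 − q)^6 + 6q(1 − q)^5. At a true rate p = 1/3:

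| h | 0 | 0.05 | 0.10 | 0.25 |
|---|---|---|---|---|
| Level accepted | 0.351 | 0.374 | 0.398 | 0.481 |
| Accepted and never paused under 11.3 | 0.264 | 0.273 | 0.281 | 0.301 |

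The second row is a simulation with 150,000 runs per cell. It assumes that all lead-in patients are eligible and that dropped DLTs are counted in 11.3. Without replacement (accepting if at most one counted DLT occurs among six treated), it stays at 0.26 for every h.

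**The case against.** The strongest reply is that the operative text already keeps the DLT. Section 11.1 counts patients treated and DLTs observed, and 11.1.2 gives all safety analyses to the safety set, which has no such gap. That stands. A reader might infer that the plan as written loses DLTs or will declare an RP2D_c on an undercount. The documents do not support this, because nowhere do they say that the 3+3 is run on the DLT-evaluable set. What remains is a faulty definition whose link to the dose rule is left unstated.

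Second, a reader might take the patient with one infusion and 8 sotorasib days missed to be out on every reading. That is also too strong. Planned doses is undefined. Section 11.2.1.4 measures compliance after allowing for adjustments that the protocol prescribes. If planned were read that way here, a directed hold would not be a shortfall and the patient would enter as a completer. That section concerns compliance only, so it does not settle the matter.

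Third, there are safeguards. In the lead-in, 11.3 has data reviewed cohort by cohort and the RP2D_c decided on all available data, so a known DLT would be before the reviewers. Section 11.1.1 allows the RP2D_c to be revised in expansion. A toxicity that requires permanent discontinuation is itself a DLT under 6.2, so a patient removed for it within cycle 1 enters by the second route. These points hold and keep the rating low. They do not repair the definition.

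**Conclusion.** The definition is wrong as written for its evident purpose, and any error it causes goes one way. The consequence is conditional: a DLT is lost only if the 3+3 is counted on the DLT-evaluable set and planned doses means the full schedule.

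The size cannot be fixed from the documents. The share affected is probably low. In 3.1.7 the dominant severe tarloxotinib toxicity is QTc prolongation (34.8%, against 4.3% for rash, 4.3% for diarrhea and 0% for nausea), and 6.5.4 states no skipped infusion at 501 to 600 msec. With h of 0.05 to 0.10 and replacement, acceptance at a true rate of one third rises from 35% to 37–40%; after the 11.3 monitoring the change is from 26% to 27–28%. The larger rise, to 48%, needs h = 0.25, for which the documents offer no support, so it should not be read as an expected effect. The point is minor.

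A separate timing issue sits beside it. Section 6.2 counts "Failure to recover from toxicities to be eligible for re-treatment within 4 weeks" as a DLT. Four weeks from even a Day 1 toxicity end on Day 29 at the earliest, outside the 28-day period. This does not bear on the gap above, but the two passages must be reconciled.

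**What to change.** In 11.1.2 and the synopsis, define the DLT-evaluable population as any lead-in patient with a DLT in the 28-day cycle 1 period, whatever doses were received and whether or not treatment stopped. Add to these the DLT-free patients who complete the period with at least 75% of planned doses. State whether 75% applies to each drug or to pooled doses, and whether planned is net of protocol-directed holds. In 11.1, say that the 3+3 is counted on this set, and whether DLT-free patients who are not evaluable are replaced. Separately, reconcile the recovery criterion in 6.2 with the 28-day observation period.

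The cost is a few sentences, with no added procedures. The downside is that a dose level may fail slightly more often than under a count on the present definition. If replacement is chosen, the lead-in could exceed its stated maximum of 18, which would then need adjusting.
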